3.1 Study Type and Design

This is an experimental study employing a prospective randomized controlled trial.

The primary outcome would be to compare the patency of arteriovenous fistula at one, three and six months.

Secondary outcomes shall include:

- To capture data regarding variables that may affect patency of arteriovenous access flow dysfunction post ultrasound-guided fistuloplasty versus fluoroscopy-guided fistuloplasty,
- To compare technical success (defined as clinical palpable thrill, radiographic finding of less than 30% recoil and ultrasonographic finding of continuous segment of dilated vein to 5-6mm and continuous flow rate of more than 500ml/min) in patients with arteriovenous access flow dysfunction receiving ultrasound-guided fistuloplasty versus fluoroscopy-guided fistuloplasty and
- To compare complication rates in patients with arteriovenous access flow dysfunction receiving ultrasound-guided fistuloplasty versus fluoroscopy-guided fistuloplasty

Patients are randomized using simple randomization method. Treatment plans are divided equally between ultrasound-guided fistuloplasty and fluoroscopy-guided fistuloplasty. An application “sealedenvelope.com” is used for this purpose. The application does this via a built in random number generator.

After assessing for eligibility, patients will be randomized equally with a ratio 1:1 to ultrasound-guided fistuloplasty group and fluoroscopy-guided fistuloplasty group.

Both interventions will be done in operation theatre to maintain sterility. After cleaning and draping the area of interest, local anaesthesia is given to the puncture site. A puncture needle is used to gain access to the arteriovenous fistula followed by a guide wire. Then, a sheath with an appropriate size is placed and a balloon catheter of adequate size is inserted over the guide wire and inflated for 2 minutes. Ultrasound is used in the subject group to monitor technical success. On table visualization of continuous segment of dilated vein to 5-6mm and continuous flow rate of more than 500ml/min signifies the end points of the procedure.

Fluoroscopy is used in the control group to assess for technical success. On table fistulogram visualization of less than 30% recoil of the target lesion signifies technical success. After a satisfactory result, a figure of 8 suture is placed with manual inflow occlusion. Post procedure, patients will be observed for any signs of haematoma or bleeding. If there are no immediate complications, patients will be discharged on the same day.

These procedures will be performed either by vascular surgeons or interventional radiologists below tabled:

OPERATOR	FISTULOPLASTY		CENTRE	DESIGNATION
	ULTRASOUND-GUIDED	FLUOROSCOPY-GUIDED		
[name] [name]	✓		University Malaya Medical Centre	Vascular surgeon
TBD		✓	University Malaya Medical Centre	Interventional radiologist
[name] [name]	✓	✓	Hospital Kuala Lumpur	Vascular surgeon

Cases with serious complications such as extravascular leak or significant pseudoaneurysm will be admitted for monitoring. If the complications are resolved then, the patient will be discharged. Follow-up may be scheduled earlier.

Follow-up will be done at two weeks, one month, three months and six months.

Assessment during follow-up includes:

- Resolution of symptoms (prolonged post dialysis bleeding or difficult access cannulation).
- Reduction of venous dialysis pressure to below predefined threshold values. (the acceptable value is less than 150mmHg)
- Measurement of the volume flow (the acceptable value is more than 500ml/min), flow characteristics (the acceptable characteristic is laminar flow) and diameter of the target lesion (the acceptable diameter is between 5-6mm) using duplex ultrasound.

[figure not shown]
In the event of a negative outcome during the first post fistuloplasty follow-up, it will be determined whether it is due to:

- a missed stenotic segment invisible to ultrasound or
- it is a case of severe stenotic segment refractory to fistuloplasty.

Patients belonging to the former category will cross-over to the fluoroscopic-guided fistuloplasty group. In the latter case, there is no reason to repeat the fistuloplasty regardless of the imaging method (ultrasound or fluoroscopy). Ideally, these particular patients should receive drug-coated balloon (DCB) fistuloplasty which is beyond the scope of this study. There is no alternative apart from switching to fluoroscopic-guided fistuloplasty.

Although patients on anticoagulants are excluded from this study, subjects may well be prescribed anticoagulants should they consult family doctors. As a precaution, a paragraph in the patient information sheet (PIS) clearly advised patients against consuming anticoagulants.

Consort Flowchart

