Study Population	All adult patients with arteriovenous access flow dysfunction in Hospital Kuala Lumpur and University Malaya Medical Centre during the period 1 July 2023 – 30 June 2024.
Study Design	A randomized controlled study. Selected subjects will be randomized into ultrasound-guided fistuloplasty and fluoroscopy-guided fistuloplasty groups in a ratio of 1:1
General Objective	To investigate patencies in patients with arteriovenous access flow dysfunction receiving ultrasound-guided fistuloplasty versus fluoroscopy-guided fistuloplasty at 6 months
Specific Objectives	
 To investigate patencies in patients with arteriovenous access flow dysfunction receiving ultrasound-guided fistuloplasty versus fluoroscopy-guided fistuloplasty at 6 months, To capture data regarding variables that may affect patency of arteriovenous access flow dysfunction post ultrasound-guided fistuloplasty versus fluoroscopy-guided fistuloplasty, To compare technical success in patients with arteriovenous access flow dysfunction receiving ultrasound-guided fistuloplasty versus fluoroscopy-guided fistuloplasty, and To compare complication rates in patients with arteriovenous access flow dysfunction receiving ultrasound-guided fistuloplasty versus fluoroscopy-guided fistuloplasty.
Study endpoints/outcomes	(a) Patency of arteriovenous fistula over a period of six months post fistuloplasty; (b) Resolution of symptoms; (c) Technical success; (d) Percentage increase in volume flow.
Sample Size	54 subjects.
Study Duration	1 July 2023 - 31 December 2024.

1. Background and Significance

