3.6 Sample Size

Based on a power of 80% ($\beta=0.2$), alpha of 0.05, a response anticipated difference of 90% in ultrasound-guided fistuloplasty group and 52.4% in fluoroscopy-guided fistuloplasty group, the calculated sample size for each group is 22 patients. Allowing for 20% dropout, a final sample size of 27 per group will be used.

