3.9 Statistical Analysis Plan

The data analysis will be done using the SPSS version 26.0 Descriptive date will be expressed as mean \pm standard deviation (SD) for numerical data and frequency (percentage) for categorical data. Independent t-test will be used to analyse the primary objective. Secondary objective will be analyzed using logistic regression. A value of $P < 0.05$ is considered statistically significant. The data collected will be analyzed using an per protocol basis.

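### Section 3.1 makes patency at one, three and six months the primary outcome, the synopsis objectives say 6 months, and nothing states which visit decides the trial

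*Combined protocol and SAP*

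**What the plan says.** Section 3.1 defines the primary outcome over three visits, unranked: "The primary outcome would be to compare the patency of arteriovenous fistula at one, three and six months".

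The synopsis differs. Its general objective ends with "fluoroscopy-guided fistuloplasty at 6 months", and its first specific objective carries the same single time point. Its endpoint (a) is worded differently again: "Patency of arteriovenous fistula over a period of six months post fistuloplasty". The objective in section 2 has no time point.

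Section 3.9 says: "Independent t-test will be used to analyse the primary objective". It sets significance at P<0.05 and names no visit, order of testing or multiplicity adjustment.

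Section 3.6 is based on "a response anticipated difference of 90% in ultrasound-guided fistuloplasty group and 52.4% in fluoroscopy-guided fistuloplasty group", with 80% power and alpha 0.05, and concludes that "the calculated sample size for each group is 22 patients", raised to 27 for dropout. It does not say which visit these rates describe.

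**The concern.** The objectives and the sizing suggest one test at 6 months, but the only sentence that defines the primary outcome names three visits. Two analysts following this plan could report different primary results from the same data.

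Two things are at stake. If the visits disagree, section 3.1 lets a one- or three-month result be presented as the primary result although the objectives point to 6 months. And if significance at any of the three visits were taken as success, the false-positive rate could exceed the stated 0.05. The documents do not state that rule, but they do not exclude it.

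**Working it through.** **1. The plan's sample size.** Inputs from section 3.6: rates 0.90 and 0.524, 80% power, alpha 0.05. Sidedness is not stated; two-sided is assumed. The pooled-variance normal formula, with mean rate p = 0.712, is

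n = [z(1−α/2)·√(2p(1−p)) + z(0.80)·√(p1(1−p1) + p2(1−p2))]² / (p1−p2)²

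- √(2 × 0.712 × 0.288) = 0.6404
- √(0.0900 + 0.2494) = 0.5826
- n = (1.960 × 0.6404 + 0.8416 × 0.5826)² / 0.376² = 21.55, so 22 per group
- Dropout: 22 × 1.2 = 26.4, so 27

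Both figures in the plan reproduce. With alpha 0.05/3 (z = 2.394) the same formula gives 28.96, so 29 per group. Section 3.6 therefore makes no allowance for three tests.

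**2. Does section 3.6 identify the visit?** It does not. The rates carry no time point, and 52.4% appears nowhere in Appendix 1. One ultrasound row there gives 90% at both 3 and 6 months. Another ultrasound row and the fluoroscopy row give 90% at 6 months but 100% at 3 months.

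**3. What the open choice could do to the error rate.** Assumptions:
- The same patency curve in both arms.
- Patency scored 0/1 and not regained once lost.
- A two-sided equal-variance t-test at each visit, p<0.05.
- 22 or 27 evaluable patients per arm.
- The three Appendix 1 rows with values at all three visits.

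For a curve S1, S3, S6, each patient falls into one of four classes: failed by month 1 (1−S1), failed in months 1–3 (S1−S3), failed in months 3–6 (S3−S6), or patent at 6 months (S6). All multinomial outcomes in both arms were enumerated exactly. With observed proportions x and y, the test statistic is t = (x−y) / √{[x(1−x) + y(1−y)]/(n−1)} on 2n−2 degrees of freedom.

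| Probability with no true difference (n = 22 / n = 27) | 100/100/90 | 100/88.1/77.6 | 96/76/53 |
|---|---|---|---|
| Month 1 significant | 0 / 0 | 0 / 0 | 0.9% / 1.5% |
| Month 3 significant | 0 / 0 | 4.8% / 5.4% | 5.1% / 4.7% |
| Month 6 significant | 4.3% / 5.1% | 5.1% / 4.7% | 4.9% / 4.2% |
| Any visit significant | 4.3% / 5.1% | 8.4% / 8.5% | 9.4% / 9.1% |
| Month 1 or 3 significant, month 6 not | 0 / 0 | 3.3% / 3.8% | 4.5% / 4.8% |
| All three significant | 0 / 0 | 0 / 0 | 0.04% / 0.06% |

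The any-visit rate equals the month-6 rate plus the rate of early-only significance. For the second curve at n = 22, 5.10% + 3.31% = 8.41%. Three independent tests would give 1 − 0.95³ = 14.3%; correlation between visits keeps the figures below that.

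With Fisher's exact test in place of the planned t-test, the any-visit rate is 0.7% to 4.4%.

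**4. Why the visit behind the rates matters.** Exact power of the planned t-test at 27 per group is 89% for 90% against 52.4%. It is 50% if 6-month ultrasound patency were 77.6% (an Appendix 1 value) against the same 52.4%. At 22 per group the figures are 83% and 41%.

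**The case against.** The best defence is that the plan already means 6 months. Section 3.1 speaks of one outcome, and its three visits match the columns of Appendix 1, so the list may be a reporting schedule. Both synopsis objectives say 6 months, and section 3.9 tests the primary objective. Wherever 90% appears in Appendix 1 it is a 6-month value, and only once is it also a 3-month value. Moreover, inflation needs a rule that the plan never states; it is absent on the flat curve and, with Fisher's test, on all three.

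Much of this is fair:
- Equal standing of the visits is inferred from the lack of ranking; the plan does not use the word.
- Section 3.9 does not say how many t-tests will be run.
- The 22 per group also comes out of a one-sided formula with continuity correction, so its reproduction fits one two-sided test without proving that design.
- The 90% leans towards 6 months.
- The 50% power figure pairs a value from an uncontrolled series with a control rate of unknown source. Two of the four 6-month ultrasound values in Appendix 1 are 90%. It shows sensitivity only.

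None of this removes the contradiction. No objective is labelled primary, section 2 gives no time point, and the one sentence that defines the primary outcome names three visits. A reader can infer 6 months only by setting that sentence aside. The plan also specifies the t-test, so Fisher's test offers no protection as written.

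**Conclusion.** The concern holds. The documents contradict themselves on what decides the trial, and no statement elsewhere resolves it. That textual finding is firm.

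The numerical consequence is conditional. Under an any-visit rule with the planned t-test, the false-positive rate is 8.4% to 9.4% on the two curves where patency falls between months 1 and 3 and again by month 6, and 4.3% to 5.1% (no real excess) on the flat one. Requiring all three visits would bring it almost to zero. These rates assume that lost patency is not regained. Section 3.1 provides for a further procedure after a negative first follow-up ("Patients belonging to the former category will cross-over to the fluoroscopic-guided fistuloplasty group"), so they are illustrative. The matter should be corrected before any outcome comparison is seen.

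**What to change.** - **Sections 3.1 and 3.9:** name 6-month patency, the visit both synopsis objectives give, as the single primary endpoint, and say that it alone is tested at P<0.05 for the primary claim. List one- and three-month patency as secondary outcomes, reported as differences in proportions with 95% confidence intervals.
- **Synopsis:** bring the wording of endpoint (a) into line.
- **Section 3.6:** state which visit the 90% and 52.4% describe. If they are not 6-month rates, restate the power at 27 per group for 6-month rates.

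The cost is wording; visits and enrolment do not change. The sponsor gives up the option of claiming primary success at one or three months alone, and the stated power may fall if the rates belong to another visit. Keeping all three visits primary with a Bonferroni split would cost more: 29 evaluable per group at the same rates, or 76.5% power with 27.

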We would like to research upon the efficacy of ultrasound-guided fistuloplasty as an alternative to fluoroscopy-guided fistuloplasty to prolong patency of patients with arteriovenous access flow dysfunction.

2. Objective

To determine the efficacy of ultrasound-guided fistuloplasty compared to fluoroscopy-guided fistuloplasty in patients with arteriovenous access flow dysfunction.

3. Methodology

Study design: Multicentre, randomized controlled trial.

Location: Hospital Kuala Lumpur and University Malaya Medical Centre.

Population: Vascular clinic patients in Kuala Lumpur Hospital and University Malaya Medical Centre.

1. Treatment group: Patients who underwent ultrasound-guided fistuloplasty for arteriovenous access flow dysfunction are assessed prospectively for a period of 6 months.
2. Control group: Patients who underwent fluoroscopy-guided fistuloplasty for arteriovenous access flow dysfunction are assessed prospectively for a period of 6 months.

Sampling method: Simple random sampling.

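### Simple randomisation of 54 patients cannot guarantee the stated equal arms of 27, and neither allocation nor analysis takes account of centre

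*Combined protocol and SAP*

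**What the plan says.** Section 3.1 names the method and, in the next sentence, claims a property of the result: "Patients are randomized using simple randomization method. Treatment plans are divided equally between ultrasound-guided fistuloplasty and fluoroscopy-guided fistuloplasty". A web application is to be used, described only as follows: "The application does this via a built in random number generator". Its list settings are not given. The same section repeats that "patients will be randomized equally with a ratio 1:1 to ultrasound-guided fistuloplasty group and fluoroscopy-guided fistuloplasty group".

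Section 3.6 states that "the calculated sample size for each group is 22 patients" and, after the dropout allowance, that "a final sample size of 27 per group will be used". The synopsis gives the total as 54.

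Section 3 names two sites: "Location: Hospital Kuala Lumpur and University Malaya Medical Centre". The operator table in 3.1 shows that they work differently. At University Malaya Medical Centre a vascular surgeon is listed for the ultrasound-guided procedure and an interventional radiologist, still to be named, for the fluoroscopy-guided one. At Hospital Kuala Lumpur the vascular surgeon entry covers both.

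Section 3.9 plans an independent t-test for the primary objective and logistic regression for the secondary one. It names no centre term in either. Blocks, strata, minimisation and a fixed list are not mentioned anywhere.

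**The concern.** The stated method and the stated result do not match. Under simple randomisation, 1:1 describes the probability for each patient, and the arm sizes are left to chance. A reader of 3.1 and 3.6 cannot tell whether 27 per arm is a design property or only an expectation, and whoever sets up the list could reasonably build either.

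Centre is the second part. The two sites have different operator arrangements, so centre may plausibly be related to patency. If the arms end up with different centre mixes, part of the observed difference would reflect centre rather than imaging. The planned analysis has nothing that would take this out.

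**Working it through.** **Inputs.** From the documents: 54 patients, 27 planned and 22 evaluable per arm, 90% against 52.4%, power 80%, alpha 0.05, 20% dropout, two centres. Assumed: a two-sided test (sidedness is not stated), 20% dropout in each arm, and centre splits of 27/27, 36/18 and 40/14 (none is given).

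**1. The plan's own figure.** With pooled variance, no continuity correction and mean proportion 0.712:

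n = [1.960·√(2·0.712·0.288) + 0.842·√(0.9·0.1 + 0.524·0.476)]² / 0.376² = 21.55, rounded up to 22 per arm.

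The unrounded value gives 21.55/0.8 = 26.9, so 27. The sample size reproduces and is not in question here.

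**2. Arm sizes under simple randomisation.** Let X be the size of one arm, X ~ Binomial(54, 0.5).

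- Exactly 27/27: C(54,27)/2⁵⁴ = 10.8%
- 24/30 or worse: 2·P(X ≤ 24) = 49.7%
- Smaller arm 22 or fewer: 2·P(X ≤ 22) = 22.0%
- Smaller arm 21 or fewer, that is below 22 before any dropout: 2·P(X ≤ 21) = 13.4%
- Central 95% range for one arm: 20 to 34

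**3. What this does to power.** Same normal approximation, with the plan's response rates:

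| Ultrasound / fluoroscopy | No dropout | 20% dropout |
|---|---|---|
| 27 / 27 | 88.5% | 80.1% |
| 24 / 30 | 87.8% | 78.9% |
| 21 / 33 | 86.2% | 76.6% |
| 33 / 21 | 87.7% | 79.7% |
| 20 / 34 | 85.5% | 75.6% |
| Average over Binomial(54, 0.5) | 87.9% | 79.4% |

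The average loss is 80.1 − 79.4 = 0.7 points after dropout.

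**4. Centre mix.** Allocation within each centre is an independent binomial. The table gives the exact probability that the share of patients from one centre differs between arms by at least the amount shown:

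| Assumed centre split | 10 points | 15 points | 20 points |
|---|---|---|---|
| 27 / 27 | 50% | 29% | 14% |
| 36 / 18 | 43% | 27% | 12% |
| 40 / 14 | 40% | 21% | 10% |

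**5. Shift in the estimate.** Shift = share imbalance × patency difference between centres. The documents give no patency by centre. With a 20-point imbalance, an assumed 10-point difference gives 0.20 × 0.10 = 2 points and an assumed 20-point difference gives 0.20 × 0.20 = 4 points. For scale, the planned effect is 90 − 52.4 = 37.6 points, and its standard error at 27/27 is √(0.9·0.1/27 + 0.524·0.476/27) = 0.112, or about 11 points.

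**6. After the change.** Permuted blocks stratified by centre, 20,000 simulated trials for each assumed split:

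- Blocks of 4: arm sizes never differed by more than 2 (26/28 at worst), and the centre share never differed by 10 points or more. Exactly 27/27 arose in 50%, 67% and 66% of trials for the three splits.
- Blocks of 4 and 6 mixed: the largest difference in arm size was 6, reached only under the 27/27 centre split and in 0.015% of trials. A centre-share gap of 10 points or more arose in at most 0.025%.

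**The case against.** **The method may only be mislabelled.** Section 3.1 states equal division twice and relies on a web application whose settings are not described, so *simple* may be loose wording for a fixed or blocked list. If so, the binomial figures do not describe this trial. That is possible and the documents do not settle it. The sentence in 3.1 needs correcting on either reading.

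**Unequal arms cost little.** A reader might infer from the 13.4% figure that the trial would be underpowered whenever an arm falls below 22. The documents do not support that: patients missing from one arm are in the other. At 21/33 power after dropout is 76.6% to 79.7%, depending on which arm is smaller, and the average loss is under 1 point. This stands.

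**Chance imbalance is not bias.** Simple randomisation is valid, and its chance imbalance is part of ordinary sampling error. With an assumed 20-point patency difference between centres and a 27/27 centre split, the standard deviation of the share difference is 0.139, so a typical shift is 0.139 × 20 = 2.8 points against a standard error of about 11. This also stands. What remains is that an avoidable source of variation is left in a small trial.

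**Centre balance was never promised.** A reader might take the equal-division wording to cover centres. It covers treatment arms only; on centre balance the documents are silent.

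**Stratifying does not cure the operator problem.** At University Malaya Medical Centre operator and arm are tied together within the centre. Neither stratification by centre nor a centre term separates them. This limits what the change can achieve.

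**Conclusion.** The contradiction holds: 3.1 and 3.6 state equal arms of 27, and the named method makes that exact split a 10.8% event. The right word is that it *cannot guarantee* the split. It would be too strong to say that the split cannot occur, or that simple randomisation is invalid.

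The consequences are modest. Power after dropout averages 79.4% instead of 80.1%, falling to 75.6% at 20 ultrasound / 34 fluoroscopy, at the edge of the central 95% range. The case for change rests on the inconsistency and on uncontrolled centre mix. The centre figures depend on assumed centre splits, and a 4-point shift needs both a 20-point share imbalance and an assumed 20-point patency difference between centres. This should be changed because it is cheap to do; it does not undermine the trial.

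**What to change.** In 3.1, replace simple randomisation with a computer-generated 1:1 list in permuted blocks of varying, undisclosed size, stratified by centre and concealed until each patient is assigned. In 3.9, include centre in the primary analysis. If a blocked or fixed list has already been set up, describe it and drop the word *simple*.

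Stratified blocks give near-equal arms, not always exactly 27/27, so 3.6 should present 27 per group as the target within a total of 54.

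The cost is a rewritten sentence or two, two lists instead of one, and one analysis term. The drawback is some predictability of assignments towards the end of a block, because operators can see which imaging each patient receives. Varying the block sizes and keeping them from the sites limits this. The tie between operator and arm at University Malaya Medical Centre needs separate treatment.

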3.3 Inclusion Criteria

NO.	INCLUSION CRITERIA	EVALUATION METHOD.
1	Patient able to comprehend English or Malay language.	Speak to patient.
2	Patient aged ≥ 18 years and ≤ 80 years.	Examine patient personal data.
3	Patient is willing to comply with protocol.	Ask the patient.
4	Native AVF that is able to provide prescribed dialysis consistently with 2 needles for $>2/3$ of dialysis sessions within 4 consecutive weeks.	Ask the patient & examine dialysis record.
5	Patient has a reasonable expectation of remaining on haemodialysis for 6 months.	Ask the patient.

6	Dampened thrill or pulsatile flow.	Palpate the arteriovenous fistula.
7	Volume flow (VF) <500 ml/min.	Ultrasound doppler measurement.
8	Severe stenosis (>50%) of arteriovenous (AV) access measured on color image and confirmed by peak systolic velocity (PSV) ratio of ≥ 3 in the inflow artery, anastomosis, or in the outflow vein.	Ultrasound doppler measurement.

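### Technical success is defined by thrill, recoil and duplex together, but the procedure text ties it to a different criterion in each arm, so as written the planned comparison cannot separate procedure from criterion

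*Combined protocol and SAP*

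**What the plan says.** The Synopsis lists among its specific objectives "To compare technical success in patients with arteriovenous access flow dysfunction receiving" one guidance method or the other, and section 3.1 repeats this as a secondary outcome.

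Section 3.1 defines the outcome once, for both arms. It joins a palpable thrill, "radiographic finding of less than 30% recoil and ultrasonographic finding of continuous segment of dilated vein to 5-6mm", and a flow above 500 ml/min.

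The description of the procedures, also in section 3.1, is arm-specific:

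- Ultrasound arm: "Ultrasound is used in the subject group to monitor technical success. On table visualization of continuous segment of dilated vein to 5-6mm", together with the flow threshold, marks the end of the procedure.
- Fluoroscopy arm: "On table fistulogram visualization of less than 30% recoil of the target lesion signifies technical success".

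Sections 3.1 and 3.8 schedule duplex volume flow and target-lesion diameter for all patients from two weeks onward, without linking them to technical success. Entry criterion 7 in section 3.3 requires "Volume flow (VF) <500 ml/min", so a baseline flow exists for everyone. Endpoint (d) in the Synopsis is "Percentage increase in volume flow".

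Section 3.9 assigns logistic regression to the secondary objective and a per-protocol basis to the analysis. It does not say which version of technical success is scored.

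**The concern.** A between-arm comparison needs the same outcome measured in both arms. Here the definition calls for radiographic and ultrasound findings together, while each arm's procedure text supplies only the finding from its own guiding modality. Comparing technical success is a stated objective, so a figure will be reported for it. If the arms differ, or do not, a reader could not tell whether that reflects the procedure, the test that each arm had to pass, or both.

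**Working it through.** No figure in the plan concerns technical success, so the main check sets the texts side by side.

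**1. Elements of the definition against the on-table text (all section 3.1)**

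| Element | Definition | Ultrasound arm, on table | Fluoroscopy arm, on table |
|---|---|---|---|
| Thrill | required | not described | not described |
| Radiographic recoil <30% | required | not described | sole criterion |
| Vein 5-6 mm on ultrasound | required | described | not described |
| Flow >500 ml/min on ultrasound | required | described | not described |

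The ultrasound arm has two of four elements described, the fluoroscopy arm one of four, and the two arms share none. Section 3.10 gives avoidance of radiation and contrast as a benefit of the study, which fits the absence of a fistulogram in the ultrasound arm.

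**2. Composite reading.** Success requires all four elements. Recoil is not described in one arm, diameter and flow are not described on table in the other, and thrill is in neither on-table text. The outcome cannot be scored from the procedures as written.

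**3. Modality-specific reading.** Write U and F for the arms. The observed difference is

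P(duplex pass in U) − P(recoil pass in F)
= [P(duplex pass in U) − P(duplex pass in F)] + [P(duplex pass in F) − P(recoil pass in F)].

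The first bracket is the procedure effect on a common criterion. The second is the effect of changing the criterion. Separating them needs the on-table duplex result in F, which is not described. Splitting on recoil instead would need a fistulogram in U, also not described. If the logistic regression in section 3.9 is meant to cover this outcome, it does not help: an indicator for criterion would be identical to the indicator for arm.

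**4. Link to the sample size.** Section 3.6 uses 90% and 52.4%, 80% power and alpha 0.05 (two-sided assumed). With pooled variance and mean proportion 0.712:

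n = [1.96·√(2·0.712·0.288) + 0.842·√(0.9·0.1 + 0.524·0.476)]² / 0.376² = 21.6, rounded up to 22 per group.

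Then 22 × 1.2 = 26.4, rounded up to 27. The plan's figures reproduce, and nothing in this point changes them.

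**5. Precision of a common measure.** For two-week volume flow as a continuous outcome, the unadjusted 95% CI half-width in SD units is t(0.975, 2n−2)·√(2/n):

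- n = 27: 2.007 × √(2/27) = 2.007 × 0.272 = 0.55 SD.
- n = 22: 2.018 × √(2/22) = 2.018 × 0.302 = 0.61 SD.

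The documents give no SD, so this cannot be put in ml/min. Adjusting for entry flow may narrow the interval, by an amount that the documents do not allow us to state.

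**The case against.** The best defence is that the on-table sentence for the ultrasound arm is a stopping rule: ultrasound monitors success, and diameter plus flow say when the procedure is finished. Only the fluoroscopy sentence names its criterion as technical success. On that view the composite definition governs scoring in both arms. This stands in part. A reader might infer that the arms are certainly scored by different tests, and the text does not establish that. But this reading leads back to the composite, whose elements are not described in either arm.

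The flowchart and the data collection form mentioned in section 3.14 were not available for this review and may record more. The point is therefore limited to the visible text, whose inconsistency would remain.

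Success judged by each modality's own criterion can be a legitimate outcome of a guidance strategy. That is fair, provided it is labelled as such and not presented as a common measure.

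A common measure also already exists, through endpoint (d) and the scheduled duplex. This limits the consequence, and it is why the repair is cheap.

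Finally, a two-week duplex is not immediate technical success. That is correct. It answers a related question, so on-table success should still be reported.

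**Conclusion.** The inconsistency within section 3.1 is real. Followed as written, the comparison of technical success is either unscorable from the described procedures or made with a criterion that coincides with the arm. The plan should be corrected on this point, but it concerns a secondary outcome; the primary patency outcome and the sample size are not affected.

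The size and direction of any bias are unknown, because the documents give no pass rates for the same result under both criteria. Two stronger readings are not supported. A reader might infer that one arm is favoured, but nothing shows which criterion is easier to meet. A reader might also look to the one row of Appendix 2 that reports both modalities. That is a case-control comparison whose definition of success is not shown, so it does not measure the effect of the criterion.

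The conclusion assumes that no further on-table measurement is specified in material not visible here.

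**What to change.** 1. Reconcile the definition and the procedure text in section 3.1. State which elements are recorded in each arm and when. No change to either arm's procedural end point is proposed.
2. Unless the same elements are recorded in both arms, report on-table success descriptively by arm, labelled as modality-specific, without a between-arm test.
3. Base the between-arm comparison of early result on duplex volume flow at two weeks, as a continuous measure in a linear model adjusted for the entry value, with a 95% CI. Section 3.9 needs a sentence for this, since logistic regression does not fit a continuous outcome.
4. Record this measurement before any cross-over decision, because the rule in section 3.1 acts "In the event of a negative outcome during the first post fistuloplasty follow-up". Analyse it by assigned arm, stated as an exception to the per-protocol basis.
5. Report it together with endpoint (d), which draws on the same flow data and is not separate confirmation. The acceptable flow and diameter values in section 3.8 may be shown as supportive.

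The cost is a change of wording, with no added procedure. The plan should state these limits:

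- It is a two-week result, not immediate technical success.
- Visits may be missed or, after serious complications, mistimed: "Follow-up may be scheduled earlier".
- Treatment of complications before the visit (section 3.11) may affect the measurement.
- No blinded duplex assessor is described.
- The section 3.8 flow and diameter values match the ultrasound arm's own on-table end point and may favour that arm. Continuous flow reduces the dependence on them but does not remove the asymmetry.
- Precision is low, as shown above.

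Keeping immediate success as the compared outcome would need a same measurement in both arms, such as a same-day duplex, which is an added procedure.
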